#### **Screening Procedure and Study Visits**

Potential participants will first undergo pre-screening by telephone to assess medical history and qualification for the study. Potential volunteers will have the opportunity to discuss the study and ask questions of the study recruiter at this time. Those who are eligible and interested in participation will attend a screening visit at the Rockefeller Hospital Outpatient Clinic.

**Screening Visit:** Study personnel will answer any questions about the study. Written informed consent will be obtained prior to conducting any study procedures. To ensure informed consent, the principal investigator or designee will discuss the following processes and explanations individually with each volunteer:

1. Pre HIV-test counseling;
2. Risk-reduction counseling including safe-sex and pregnancy avoidance counseling;
3. That a sexually active volunteer should use a reliable form of contraception throughout the study.
4. For Arm III, study personnel will request authorization from the participant to obtain their medical records as possible and/or speak to the treating provider from the time of virus infection. Participants will be asked to sign the HIPPA Compliant Authorization for Release of Medical Information.

If the volunteer consents to participate, site personnel will:

- Perform complete medical history (including concomitant medication);
- Perform a general physical examination including height, weight, vital signs (pulse, respiratory rate, blood pressure and temperature), examination of skin, respiratory, cardiovascular and abdominal systems, and an assessment of cervical and axillary lymph nodes;
- Safety labs will be drawn (WBC with differential, RBC, hemoglobin/hematocrit, platelets, Na, K, Cl, CO2, bun/creatinine, glucose, total and direct bilirubins, alkaline phosphatase, AST, ALT and urinalysis), as well as serologies -Hep BsAg and HCV for all Groups, for Groups 11-14 additional serologies will be performed for dengue and chikungunya viruses to ensure eligibility and vaccine safety. Rapid point of care (POC) saliva test will be performed to test for HIV.
- Perform a pregnancy test for all female volunteers;

**Day 0, Vaccination Visit:** Prior to vaccination, site personnel will:

- Answer any questions about the study;
- Review interim medical history (including concomitant medications);
- Review safety laboratory data;
- Review the informed consent form administered at screening visit with volunteer;
- Perform a physical examination including vital signs (pulse, respiratory rate, blood pressure and temperature), examination of skin, respiratory, cardiovascular and abdominal systems, and an assessment of cervical and axillary lymph nodes; as well as an assessment of axillary lymph nodes and any further examination indicated by history or observation;
- Risk-reduction counseling including safe-sex and pregnancy avoidance counseling;
- Safety labs will also be drawn prior to vaccination.
- Research bloods (81mL) will be drawn.
- Perform a point of care pregnancy test for all female volunteers and obtain results prior to vaccination;
- Perform baseline assessment of the site of injection and evaluate and record any systemic symptoms;
- Each participant will then receive a vaccination with one of the seven FDA approved vaccines. Participants will be monitored in the clinic for any vaccination reactions. Vital signs will be performed pre and post vaccination.
- Presence or absence of local and/or systemic reactogenicity events, as well as any other event that occurs, will be recorded post vaccination.

**Day 7:**

- Safety labs will be drawn.
- Research bloods (81mL) will be drawn.
- A targeted physical examination including vital signs (pulse, respiratory rate, blood pressure and temperature), as well as an assessment of axillary lymph nodes and any further examination indicated by history or observation will be performed.
- Perform a point of care pregnancy test for all female volunteers.

**Weeks 3, 5, 7, 9, 12:**

- Vital signs (pulse, respiratory rate, blood pressure and temperature) will be taken.
- Research bloods (20-170mL) will be drawn.
- Perform a point of care pregnancy test for all female volunteers.
- Groups 11-14 will not have bleeds done at week 5,7,9,12 or thereafter.

During follow up visits at day 7 and weeks 3, 5, 7, 9 and 12, study participants will receive pregnancy testing prior to sample collection because pregnancy is known to alter Fc glycan composition and would thus significantly confound study results. Volunteers with positive pregnancy tests will be discontinued from further participation in the study.

***Withdrawal from the study (Early Termination)***

Volunteers may be withdrawn from the study permanently for the following reasons:

1. Volunteers may withdraw from the study at any time if they wish to do so, for any reason.
2. Following an adverse event at the discretion of the investigator (or designee).

***Blood Collection***

Venous blood will be collected at study visits, usually from the antecubital fossa. Up to 20-170mL will be collected at study visits. At no time will the total volume of blood collected exceed 550 mL over an 8-week period. The total blood volume over the 12 week study period is 615mL. The volume of blood was increased to 615mL to conduct exploratory studies that are indicated by preliminary data from the influenza virus vaccine cohort. We have seen that there are modifications in IgG Fc glycan content induced by vaccination and that glycan composition may correlate with the avidity of vaccine-elicited IgGs. As a follow-up to these observations, we will evaluate how specific glycan modifications may correlate with activation and function of a variety of different peripheral blood cell types, some of which are found in extremely low frequency, such as DCs and CD4 follicular T helper cells. These studies will require PBMCs from an additional 80mL of blood at each of three time points in the study timeline: baseline, day 7 and week 3. This is now reflected in the total blood volume of 615mL. All specimens will be handled and processed in the GLP Processing Lab of the Laboratory of Cellular Physiology and Immunology. Only a code number will identify the samples. Frozen PBMCs, plasma and serum will be stored at RU.

***Reimbursement***

Volunteers will be compensated \$75 for their vaccine visit, \$35 for the follow-up blood draw visits except for the final visit, for which participants will be compensated \$75. Reimbursement will be outlined in the informed consent form.

It is expected that volunteers for Arm III will be more likely to live outside of the immediate area, as patients with prior flavivirus or alphavirus infection are relatively rare. In consideration of anticipated

travel time for volunteers in Arm 3, participants will receive \$25 for the screening visit, and compensation will be a minimum of \$100 for each visit.

#### **Sample preparation and laboratory analysis**

Leukocytes will be separated from plasma, red blood cells and platelets by Ficoll (GE) gradient centrifugation. Plasma, serum and cells will be frozen for analysis at a later time. The serum will be characterized for cytokines using luminex multiplex assays and ELISAs. Serum will also be used to extract IgGs for analysis by ELISA, western blot and by mass spec for specificity and Fc glycan content. Fc glycans will be analyzed following isolation of antigen-specific IgGs by affinity chromatography. Vaccine preparations or purified proteins/polysaccharides will be coupled to sepharose beads as previously described for extraction of specific serum IgGs (11-14). Fc glycans from antigen-specific IgGs will be isolated by digestion with EndoS enzyme for subsequent mass spec analysis of the Fc glycan (15). Vaccine preparations for research use will be obtained from the RU pharmacy, purified influenza virus antigens will be obtained from the Biodefense and Emerging Infections Research Resources Repository, purified pneumococcal polysaccharides from ATCC. Serum IgGs will also be used in in vitro and in vivo (murine) assays in the laboratory to assess the functional consequence of Fc glycan modifications during infection with influenza viruses or with Streptococcus pneumonia (16-18). Mice humanized for FcgRs will be used for in vivo studies using human IgGs (19). RNA will be extracted from samples collected in PAXgene tubes for analysis related to specific modifications of IgG Fc glycans occurring post-vaccination.

In addition to the above samples, we will study existing serum samples from a study performed at NIAID in which healthy volunteers were infected with influenza virus in a controlled hospital setting. Samples will be obtained from an existing collection from approximately 30 study participants from the following time points: pre-infection, day 3 post infection, day 7 post infection, week 3 post infection and week 5 post infection (for a total of 150 samples). Subjects in the infection study performed at NIAID consented to future use of samples for scientific investigation and samples will be de-identified without any accompanying information containing patient identifiers. Laboratory analysis of the serum samples will follow the same protocol as described above for sera collected under the vaccination protocol. Investigators from the NIAID will not be collaborating on this research; they will not be receiving any data derived from this study, will not participate in data analysis, and will not co-author any publications stemming from this study.

In addition to the above samples, we will study existing serum samples from a study performed through Emory University in which patients with diagnosed dengue virus infection had blood drawn. Samples will be obtained from an existing collection from approximately 10 study participants from the following time points: acute infection, post-defervesence, and 1-2 months post-infection. Subjects in this study consented to future use of samples for scientific investigation and samples will be de-identified without any accompanying information containing patient identifiers. Laboratory analysis of the serum samples will follow the same protocol as described above for sera collected under the vaccination protocol. Investigators from Emory will not be collaborating on this research; they will not be receiving any data derived from this study, will not participate in data analysis, and will not co-author any publications stemming from this study.

With the August 2018 amendment, de-identified research samples (serum) will be received from collaborators from the Massachusetts General Hospital ([name] and [name]) obtained from patients with IgG4 related diseases. A total of approximately 20 research samples will be received in the [name] laboratory. There will be no attempt on the part of the Principal Investigator at the Rockefeller University to link the identity of the participant to the research sample nor will the collaborators at Massachusetts General Hospital provide the code to the identity of the participant sample. The MGH collaborators will receive the data derived from this study as it relates to their research samples as needed.

#### **12.10 \* Data Analysis**

Describe method(s) of data analysis.

In order to find evidence that IgG Fc glycan composition changes from pre- to post-vaccination, we will apply two-sided t-tests and wilcoxon

tests for paired samples with significance fixed at 5% when evaluating change in abundance of specific saccharide units. For each vaccine antigen, we will be comparing pre- (day 0) to post- (day 21) vaccination IgG Fc glycan composition in order to see which vaccines elicit significant saccharide modifications. We will apply the same analysis to data obtained through study of samples taken prior to and at day 21 post influenza virus infection. For the analysis of the time course experiment and comparison across different groups, we are going to use Repeated Measures ANOVA, descriptive graphics and possibly fitted curves that may bring information about changes in time. Depending upon results in humans (Aims 1 and 2), in vivo experiments will be carried out in mice. For this stage, our Biostatistical Core will be consulted about the appropriate design and analysis of the experiments.

**12.11 \* Explain the rationale for the choice of statistical measures and the number of participants proposed for the study, including the power calculations when applicable.**

Sample size evaluation was carried out to provide 80% power and 5% of significance for a two-tailed paired t-test to verify pre-post differences in the relative abundance of sugars. For each one of the specific saccharides to be measured, we expect an effect size a 10% change in relative abundance, with a standard deviation of 4.4% - this is based on data presented in Selman et al. (2012). Selman et al. evaluated changes in IgG1 Fc saccharide abundances (galactosylation, fucosylation and sialylation) following influenza vaccination of 10 Caucasian adults. Based on their data, we selected the highest standard deviation, which occurred in abundance of sialylation. Adjustments for error multiplicity were done by a Bonferroni-Correction that reduced the individual significance levels to be 0.017 (0.05 significance divided by 3 sugars evaluated). Another adopted measure for taking into account the uncertainty about the standard deviation was to inflate that estimate by multiplying it by 1.30. This caused our standard deviation to increase to 5.72% from 4.4%. After all described procedures, using the function *n.ttest* in package *samplesize* in R, the initial evaluated sample size resulted in n=7 per group. It is important to emphasize that only samples from subjects with a two-fold increase in vaccine-specific antibody titer will be further analyzed for IgG Fc glycan saccharide composition. Thus, the evaluated sample size was increased to n=10 to accommodate the possibility of having a 20% rate of vaccine non-responsiveness and also the expected rate of volunteer drop-off (10%).

**ARM III:** We have preliminary data on the abundance of afucosylated glycans on anti-dengue envelope protein IgG

from patients with acute dengue virus infection- the data are from one time point (acute infection) and we are comparing two groups: patients with dengue hemorrhagic fever (the severe disease) vs. dengue fever (the mild form of the disease). The maximum coefficient of variation between the two groups was 55%. Assuming that for the present study the populations to be sampled will have the same variability, a sample size of n = 25 (per group) would guarantee 80% power at 5% significance to detect a minimum Fold-Change (FC) of 1.5 (50% increase) when comparing two independent groups with an unpaired two-sided t-test. In this calculation, we are taking into account that 5 pairwise comparisons will be performed, thus the test-wise significance level will be reduced to 0.01.

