**12.7 \* Primary Outcome(s)**

Indicate which **variable(s)** will be assessed to judge the primary specific aim. Give measurement units, if applicable.

**Determination of saccharide components of the IgG Fc glycan pre- (day 0) and post- (day 7 and day 21) vaccination with different vaccines and before, during and following influenza virus infection:**

- The degree of galactosylation, fucosylation and sialylation of pre- vs. post- vaccination Fcs determined by lectin blot (*Erythrina cristagalli*, *Aleuria Aurantia Lectin* and *Sambucus nigra* lectins specific for galactose, fucose and 2,6-sialic acid, respectively).
- Characterization of glycan composition by mass spec analysis.

**Determination of the role of route of antigen exposure, age of the patient, or past flavivirus or alphavirus infection in regulation of Fc glycan modifications.**

- Using three influenza virus vaccines (two inactivated that are administered either intramuscularly or intradermally, and one live that is administered intranasally) we will compare how the route of administration affects modifications of the Fc glycan by western blot and mass spec analysis.
- By comparing vaccine responses in patients < 65 or ≥65 of years of age we will determine how age regulates post-vaccination modifications of the Fc glycan.

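### Section 12.10 tests each sugar at 5% with two paired tests and no rule on which decides, while 12.11 sizes the groups on a paired t-test alone at 0.017 per sugar

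*Combined protocol and SAP*

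**What the plan says.** Section 12.10 (Data Analysis) opens with the evidence for a pre-to-post change: "we will apply two-sided t-tests and wilcoxon" "tests for paired samples with significance fixed at 5% when evaluating change in abundance of specific saccharide units". It fixes the contrast, "For each vaccine antigen, we will be comparing pre- (day 0) to post- (day 21) vaccination IgG Fc glycan composition", with the aim of learning which vaccines produce a significant change. The same analysis is applied to the influenza-infection samples. The section mentions no multiplicity adjustment, and has no rule for the case where the two tests disagree.

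Section 12.11 (sample size) starts from "80% power and 5% of significance for a two-tailed paired t-test" and then describes a "Bonferroni-Correction that reduced the individual significance levels to be 0.017 (0.05 significance divided by 3 sugars evaluated". Only the paired t-test is powered. The result is 7 evaluable participants per group. This is raised to 10 for 20% vaccine non-response and 10% drop-off, because only participants with a two-fold titre rise are analysed.

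Section 12.7 (Primary Outcomes) lists the glycan measurements "pre- (day 0) and post- (day 7 and day 21) vaccination with different vaccines", by lectin blot and by mass spectrometry. Section 12.10 assigns the time course and the between-group comparisons to repeated-measures ANOVA, graphics and possibly fitted curves.

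**The concern.** The two sections give different thresholds for the same comparison. An analyst working from 12.10 alone would test galactosylation, fucosylation and sialylation each at 5%, and could report whichever of two tests was significant. An analyst working from 12.11 would use one test at 0.017. A sugar with a p-value between 0.017 and 0.05 would count as changed under one section and not under the other.

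What is at stake is the main question of Aim 1, which vaccines modify the Fc glycan. The groups were enlarged to pay for a correction that the analysis section does not apply. The choice between t-test and Wilcoxon is also left open until results are known.

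**Working it through.** **Inputs.** From 12.11: expected change 10 points; SD 4.4 inflated by 1.30 to 5.72; 80% power; two-sided paired t-test; level 0.05/3; losses of 20% and 10%. From 12.10: 5% level, two tests, Day 0 against Day 21. From 12.9: groups of 10, except Group 2 with 25; about 30 infection-study participants.

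**1. The plan's own figure.** Standardised change d = 10/5.72 = 1.748. Exact paired t-test power (noncentral t, n − 1 degrees of freedom, noncentrality d√n):
- at 0.05/3: 73.8% for n = 6 and 85.9% for n = 7, so n = 7, as stated (using 0.017 gives 74.2% and 86.2%, also n = 7);
- at 0.05: 65.1% for n = 4 and 82.8% for n = 5, so n = 5.

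Inflation: 7/(1 − 0.30) = 10.0, or 7/(0.8 × 0.9) = 9.7, rounded up to 10. The stated 7 and 10 both reproduce, and the 7 depends on the corrected level.

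**2. Error if 12.10 is followed literally.** For one vaccine that changes none of the three sugars, the chance of at least one significant sugar with one test at 5% each is:
- independent sugars: 1 − 0.95³ = 14.3%;
- upper bound under any dependence: 3 × 5% = 15%;
- perfectly correlated sugars: 5%.

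If either the t-test or the Wilcoxon may count, simulation of normal changes (100,000 samples for each n of 6, 7, 8 and 10) gives 5.3–5.8% per sugar. For three independent sugars that is 15–16%. Most of the excess comes from the three uncorrected sugars; the second test adds about 1–2 percentage points.

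**3. Error with the 12.11 level.** One test per sugar at 0.05/3 gives 1 − (1 − 0.05/3)³ = 4.9% for independent sugars, with a bound of 5%. Lowering the level without naming a deciding test does not quite restore this. If either test may count at 0.05/3, the simulated three-sugar figure is 4.8% at n = 6, 6.2% at n = 7, 5.8% at n = 8 and 5.3% at n = 10.

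**4. Which test can serve as the deciding one.** The smallest exact two-sided signed-rank p-value is 2/2ⁿ: 2/64 = 0.031 at n = 6 and 2/128 = 0.0156 at n = 7. At 0.017 the Wilcoxon therefore cannot be significant with 6 or fewer evaluable participants, and with 7 it needs all seven changes in the same direction. With 10 enrolled and a 0.72 chance of being evaluable (0.8 × 0.9, assuming independent losses), 6 or fewer occurs in 29.8% of groups; at 0.70 it is 35.0%. The limit is not a practical issue for Group 2 or for the infection samples.

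**The case against.** The strongest reply is that the 5% in 12.10 is the overall level. Section 12.11 uses 5% that way twice: for the paired design, where it is then divided to 0.017, and for Arm III, where it is reduced to 0.01 for five comparisons. Its title also covers the rationale for the statistical measures, so it can be read as governing the analysis. On that reading the correction exists and 12.10 merely fails to repeat it. This is plausible, and it means one cannot say that the plan intends uncorrected testing. It does not settle the matter. Section 12.10 attaches the 5% to tests on specific saccharides and does not refer to 12.11, and neither section says what role the Wilcoxon has.

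Three stronger readings are tempting but not supported:
- A reader might infer from the Wilcoxon limit that the groups of 10 are underpowered. No section makes the Wilcoxon decide at 0.017. The powered test is the paired t-test, and its sample size is correct.
- A reader might multiply 10 vaccine groups by 3 sugars and quote 1 − 0.95³⁰ = 78.5%. The plan defines no such family and asks its question vaccine by vaccine. Section 12.9 reports glycan changes already seen after influenza vaccination, so a global null is implausible. The correction in 12.11 would not control that family either: 1 − (1 − 0.05/3)³⁰ is about 40%.
- A reader might infer that Day 7 has no planned analysis, or that it and the lectin blot should be demoted. Day 7 plausibly falls under the repeated-measures time course, and 12.7 lists both as primary.

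**Conclusion.** The mismatch is real. Section 12.10 states 5% with two tests and no correction; 12.11 states one test at 0.017. Taken literally, 12.10 allows up to about 14–15% false-positive risk per vaccine, or 15–16% if either test may count, where the sample size assumed 5%. These figures take all three sugars as unchanged by the vaccine and any significant sugar as a positive finding, a rule that 12.10 leaves open rather than states. The 14.3% and the 15–16% also assume independent sugars; correlation lowers them. If the 5% was meant as the overall level, the defect is an omission from 12.10, and the same edit repairs it. The sample size needs no change.

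**What to change.** In 12.10:
- replace the 5% with a two-sided level of 0.05/3 per sugar, or Holm over galactosylation, fucosylation and sialylation, within each vaccine;
- name the paired t-test for Day 21 minus Day 0 as the deciding test, since the sample size rests on it, and make the Wilcoxon a sensitivity analysis. The Wilcoxon should not decide at 0.017 in the groups of 10;
- state that error is controlled per vaccine and not across vaccines.

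The status of Day 7 and of the lectin blot in 12.7 need not change for this.

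The cost is wording, with no added participants or visits. P-values between 0.017 and 0.05 no longer count as significant, which the sample size already assumed. Section 12.9 shows that influenza-vaccine data have already been examined, so for those groups the clarification should be reported as made after data were seen.

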**The study will occur in four phases:**

**Phase 1:** Volunteers will be recruited to receive influenza vaccines (Groups 1, 2, 7, 10). Recruitment for Groups 1 and 7 will occur simultaneously and volunteers will be enrolled sequentially - enrollment into Group 1 will be given priority over Group 2 because the intradermal vaccine preparation for the 2012-13 influenza season will expire earlier than the intramuscular preparation (April 2013 vs. June 2013). Volunteers will be recruited to receive the Flumist influenza vaccine (Group 10) beginning fall of 2013.

**Phase 2:** Volunteers will be recruited to receive one of the pneumococcal vaccines (Groups 3, 4, 8, 9)

- these subjects will be recruited simultaneously and will be randomized to receive either the Pneumovax or Prevnar vaccines.

**Phase 3:** Volunteers will be recruited to receive one of the meningococcal vaccines (Groups 5 and 6) - these subjects will be recruited simultaneously and will be randomized to receive either the MPSV4 or Menveo vaccines.

**Phase 4:** Volunteers will be recruited for Arm III of the study to receive the Fluzone intramuscular vaccine (Groups 11-14)

Study participants will not be blinded. During the analysis phase, samples will be coded so that the precise vaccine administered within each phase is unknown.

Study visits will be scheduled as follows for groups 1-10: screening, day 0 (within 4 weeks of screen), day 7 safety visit, and weeks 3, 5, 7, 9, and 12. On Day 3-4, a telephone call will be made to check on subject's medical status.

Groups 11-14 will be scheduled as follows: day 0 (within 4 weeks of screen), day 7 safety visit, and week 3. We will not collect samples at weeks 5, 7, 9 or 12 for Groups 11-14 because our existing data on intramuscular Fluzone immunization from Group 2 demonstrate that the major Fc glycan modifications occur during the first 3 weeks following vaccination.

**We do not anticipate any safety issues related to this protocol as all vaccines to be used have been FDA approved and all study participants are healthy adults.**

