## 25.0

### Toxicity Management and Stopping Rules

**25.1 \* Describe any drug toxicity or other conditions under which the participation of a participant or the conduct of the study would be stopped in order to maximize safety (e.g., toxicity management and stopping rules):**

Not applicable.

\* Indicate withdrawal criteria and procedures below:

Volunteers may be involuntarily withdrawn from the study if:

- They fail to keep appointments.
- Termination or cancellation of the research study by the investigator or the Rockefeller University Institutional Review Board.
- There is a significant adverse event to the participant or to others in the study,

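### Classical Repeated Measures ANOVA discards anyone with an incomplete visit series; a mixed model on named visits would keep their data

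*Combined protocol and SAP*

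**What the plan says.** Section 12.10 divides the analysis in two. Within each vaccine, "we will be comparing pre- (day 0) to post- (day 21) vaccination IgG Fc glycan composition", by two-sided paired t-tests and Wilcoxon tests. The other analyses rest on one sentence: "For the analysis of the time course experiment and comparison across different groups, we are going to use Repeated Measures ANOVA", supported by descriptive plots and, optionally, fitted curves. Neither 12.10 nor any other section says which form of the ANOVA is meant, which visits enter each comparison, or what happens when a visit is missing.

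The visit schedules are in section 12.9:
- Groups 1-10: day 0, day 7 and weeks 3, 5, 7, 9 and 12.
- Groups 11-14 (Arm III): day 0, day 7 and week 3 only. The plan says "We will not collect samples at weeks 5, 7, 9 or 12 for Groups 11-14" and gives a reason, namely that the main changes in Group 2 fell in the first three weeks.
- Groups 1 and 2 only: one further visit at 6 to 12 months.

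Several provisions lead to incomplete series. Section 12.11 expects 10% drop-off. The early-termination list in 12.9 says "Volunteers may withdraw from the study at any time if they wish to do so, for any reason" and adds withdrawal after an adverse event at the investigator's discretion. Section 12.9 also discontinues participants with a positive pregnancy test. Section 25.1 lists, among reasons for which a volunteer may be withdrawn, "They fail to keep appointments"; the early-termination list in 12.9 does not contain that reason.

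**The concern.** Classical Repeated Measures ANOVA needs a complete row of visits for each person. Someone who attends day 0, day 7 and week 3 but misses week 7 leaves a seven-visit analysis altogether, although the samples that matter most were taken.

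Section 12.7 lists route of administration, age and past infection among the primary outcomes, and 12.10 gives comparisons across groups to this method. Most groups have ten people. Losing one of them is a visible loss of information, and the estimate then applies only to people who kept every appointment. If attendance is related to the immune response or to tolerability, that selection can also bias the comparison.

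**Working it through.** **1. The plan's own sample size.** Section 12.11 asks for "80% power and 5% of significance for a two-tailed paired t-test", with a change of 10 points, an inflated SD of 4.4 × 1.30 = 5.72, and a per-test level of 0.017 (0.05/3). The exact noncentral-t power of the paired test is 0.742 at n = 6 and 0.862 at n = 7, so n = 7 reproduces. Inflation for 20% non-response and 10% drop-off gives 7/(0.80 × 0.90) = 9.7, or 7/(1 − 0.30) = 10.0. Both round up to the plan's 10.

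**2. What that allowance covers.** A group of ten is expected to yield 10 × 0.80 × 0.90 = 7.2 evaluable people, about the 7 that the paired test needs. That test uses only the day 0 and day 21 samples. The allowance was not derived for a complete seven-visit series, and no power is stated for the Repeated Measures ANOVA.

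**3. How the two methods treat a gap.** In a software check on simulated data (8 people, 7 visits, one empty cell), the classical routine refused to run because the data were unbalanced, so that person would have to be deleted or imputed. A mixed model used all 8 people and 55 of the 56 observations. The classical routine restricted to day 0, day 7 and week 3 on complete data ran normally.

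**4. Size of the loss.** The documents give no rate of single missed visits. Assume independent misses at a rate m per post-baseline visit, on top of the 10% drop-off, with day 0 always present. Then, per ten-person group:
- complete over all seven visits (six after baseline): 7.2 × (1 − m)^6
- complete over day 0, day 7 and day 21 (two after baseline): 7.2 × (1 − m)^2
- with a day 21 sample: 7.2 × (1 − m)

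| Assumed m | Complete, 7 visits | Complete, day 0/7/21 | Day 21 sample present |
|---|---|---|---|
| 2% | 6.4 | 6.9 | 7.1 |
| 3% | 6.0 | 6.8 | 7.0 |
| 5% | 5.3 | 6.5 | 6.8 |

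Against those with a day 21 sample, the loss is about 0.7 to 1.5 people per group on the full grid, and about 0.1 to 0.3 on the three visits that 12.7 names for the vaccination outcome.

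**5. The 10% drop-off.** All three columns start from 7.2, so the plan's drop-off does not drive the differences in the table; the assumed m does. Drop-off matters in another way: the classical method uses nothing from people who leave early, whereas a mixed model can use the visits they attended. At most that recovers the gap between 8.0 responders and 7.2 per group. How much of it depends on when people leave, which the documents do not say.

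**The case against.** **The plan may not mean the classical form.** It names no form, and the possible fitted curves could use partial series. This stands as far as it goes, but an unspecified form and an optional curve are no commitment. The usual reading of the name is the classical one.

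**The main test is protected.** This stands. The paired comparison of day 0 with day 21 is separate, a missed week 7 visit does not touch it, and n = 10 already allows for drop-off there. The point concerns only the time-course and between-group analyses.

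**The loss is small on the visits that matter.** This stands in part. Section 12.7 names day 0, day 7 and day 21 for the vaccination outcome, and on those visits the loss is a fraction of a person per group. The larger figures apply only if all seven visits enter the model, and 12.10 does not say which visits do.

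**Stronger readings that the documents do not support.**
- A reader might infer that Arm III's shorter schedule creates missing visits, or bars its participants from a model with Group 2. It does neither. The three visits are planned and complete, Group 2 has the same three, and an analysis on those visits runs. Section 12.11 also sizes Arm III on an unpaired t-test. What is missing is a statement of the common visit set.
- A reader might attach a power loss to the between-group comparisons by assuming two small equal groups and a 10-point difference. Section 12.11 gives the 10 points for within-person change, not for a difference between groups. Group 2, the intramuscular comparator for route and for age under influenza vaccine, has 25 people, or about 25 × 0.72 = 18 evaluable.
- A reader might take 25.1 to remove anyone who misses one visit. The wording is permissive and speaks of appointments in the plural.

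**Conclusion.** The point holds as a specification gap with an inexpensive remedy. Section 12.10 names a method whose classical form discards incomplete series, the plan's own provisions make such series likely, and no rule covers them. Results would rest on full attenders in groups with about seven evaluable people.

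The size is uncertain. It rests on the assumed 2% to 5% rate of independent misses and on which visits enter the model, neither of which the plan states. Nothing here undermines the paired pre-post test, the sample size of 10 derived for it, or the Arm III schedule.

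**What to change.** In section 12.10, replace Repeated Measures ANOVA with a likelihood-based linear mixed model for repeated measures, and state:
- fixed effects for visit, group and group-by-visit;
- restricted maximum likelihood with a small-sample degrees-of-freedom correction;
- an unstructured within-person covariance, with a simpler structure named in advance in case it does not fit;
- use of all available visits, with the between-group contrast at day 21;
- Arm III compared with Group 2 on their shared visits only (day 0, day 7, week 3);
- the 6-12 month visit, collected only in Groups 1 and 2, kept out of comparisons with other groups;
- the assumption that missingness depends only on observed data, with a complete-case analysis as a sensitivity check.

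Separately, the withdrawal lists in 12.9 and 25.1 differ and should be reconciled.

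The cost is a few lines of text and standard software, with no change to sample size or visits. The one small drawback is that a covariance structure must be chosen with small groups, and a simple one may be all that the data support.
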